- 4. To determine the longitudinal effect of ETI on nutrition, gastrointestinal symptoms, gut inflammation and pancreatic function in children and adults with CF over an additional period of 5 years.
- 5. To determine the longitudinal effect of treatment with ETI on CF liver disease in children and adults with CF over an additional period of 5 years.
- 6. To determine the longitudinal effect of treatment with ETI on antibiotic treatment of pulmonary disease in children and adults with CF over an additional period of 5 years.
- 7. To determine the longitudinal changes in mental health outcomes associated with the use of ETI in children and adults with CF over a period of 5 years.

BACKGROUND AND SIGNIFICANCE

Cystic Fibrosis

Cystic fibrosis (CF) is the most common progressive life threatening genetic disease in Caucasians(1). Approximately 80,000 people in the world and 1,200 people in Ireland have CF, almost half of whom are children (CFRI annual report 2016). CF is a multisystem disorder caused by a mutation in a gene that encodes cystic fibrosis transmembrane conductance (CFTR) protein. Lung disease is responsible for the majority of the morbidity and mortality in CF. Predicted survival for individuals with CF currently exceeds forty years, however the current mean age of death is still in the twenties(1). Medications that can modulate the natural history of CF and minimize, or even prevent, the development of life-threatening consequences of CF have been long sought after, particularly if these can be commenced in young children prior to the development of organ damage and irreversible disease.

CF Lung Disease

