Sweat tests will be carried out on all individuals prior to initiation of treatment and then at 6 months after treatment, at one year and at two years for the parent study, and annually in the extension study. Sweat will be collected using the Macroduct sweat collection system as per manufacturer's instructions using pilocarpine iontophoresis to induce sweating. Sweat tests will be performed on both arms. Sweat will be stored in 0.2ml

P.I. [name]

PCR tubes and immediately transferred to the laboratory and frozen at -80°C. Sweat chloride will be analyzed in all stored sweat samples in batches by the Chloro-check Chloridometer (EliTech Group Inc.) at all sites.

Nutritional Indices

Height and weight will be measured at three monthly intervals throughout the duration of the parent study at each out-patient visit, and annually during the extension study. Height, weight and BMI z-scores will be calculated from these measurements.

Patient Reported Outcomes – Respiratory Symptoms

CFQ-R (including the CFQ-R treatment burden subscale) will be administered to study participants every six months during the parent study and annually during the extension study. Scores in all domains of CFQR will be compared between baseline and follow up visits.

Investigational Medicinal Product (IMP)

The IMP for this trial is ETI (EU/1/20/1468/001). This IMP is licenced for use in the United Kingdom and will be administered to study subjects in line with the prescription and in line with the SmPC. To be enrolled in the Parent Study, all patients were prescribed ETI. The decision to implement treatment with IMP is made completely independently of the decision to enter subjects into the study. If a patient experiences a drug interruption, discontinues ETI and/or is prescribed TEZ/IVA (EMEA/H/C/004682), LUM/IVA (EMEA/H/C/003954) or IVA (EMEA/H/C/002494) after enrolment, they can continue trial participation. IMP will be dispensed in accordance with usual clinical practice (i.e. by hospital pharmacy/community pharmacy) and therefore no additional labelling, QP batch release or drug accountability is required.

Recording and reporting of adverse events and reactions

Definitions

Torm	Definition					
Term						
Adverse Event (AE)	Any untoward medical occurrence in a patient or clinical trial					
	subject administered a medicinal product and which does not					
	necessarily have a causal relationship with this treatment.					

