The PROMIS Pediatric Anxiety Scale (Short Form – 8a) and Depressed Mood Scale (Short Form – 8a) are brief self-report measures that can be administered to children from the age of 8 years, providing discreet measures of depressed mood and anxiety for younger children (153). This will represent the first self-report of younger children's emotional experience of CF in a large-scale study (118, 153). In addition to the parent-report PSC Attention subscale, neurocognitive functioning will be measured by the PROMIS Pediatric Cognitive Function Scale (Short Form 7a). This is a brief self-report measure of children's experiences of attention, memory, and comprehension, which is validated for use from the age of 8 years. There is also an adult version (Short Form 8a) which will be used for patients over the age of 18 (153). Body image will be assessed using a three-item questionnaire designed for this study, completed by children from the age of 8 years.

A linear mixed model for each of the mental health outcomes will be used to investigate impacts of patient characteristics over time. Fixed effects in the model will be: age at ETI initiation, genotype, sweat chloride level, nutritional status, caregiver burden scores, number of treatments, year. The model will use random intercept for patient.

The RECOVER distress protocol as shown in Table 10 below will be utilised as needed for participants completing questionnaires.

Table 10: Distress protocol for participant completing interview or questionnaires. (154, 155)

Statistical Analysis

Statistical support and analysis will be provided by CFRI for the parent study and by the Research Data Science team at CHI in conjunction with the Data Science Centre in RCSI for the extension study. Data management and analysis will be carried out using SAS version 9.3 for the parent study and STATA V17.0 for the extension study.

Sample Size and Power for the Parent Study

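### The mental health model for extension Aim 7 sets year beside covariates of unstated timing, and no year effect is named as the longitudinal change the aim asks for

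*Protocol*

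**What the plan says.** The aim, in the protocol's Hypothesis and Specific Aims for Extension Study, is "To determine the longitudinal changes in mental health outcomes associated with the use of ETI"; the stated horizon is 5 years.

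The section Specific Aim 7 for Extension Study – Mental Health gives one model: "A linear mixed model for each of the mental health outcomes will be used to investigate impacts of patient characteristics over time". Its fixed effects are genotype and age at ETI initiation, together with "sweat chloride level, nutritional status, caregiver burden scores, number of treatments, year". On random effects it says: "The model will use random intercept for patient". Of the covariates that can change over time, only age is tied to a date (ETI initiation).

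On when things are measured:
- Sweat chloride is taken "prior to initiation of treatment and then at 6 months after treatment, at one year and at two years for the parent study, and annually" (Sweat Chloride, under Core Data to be Collected); the yearly tests are those of the extension.
- Height and weight are taken three-monthly in the parent study and yearly in the extension (Nutritional Indices).
- The mental health questionnaire is marked in years three to seven only (Table 14). The background section on mental health confirms that these outcomes were not part of the parent study at its start.
- Table 14 has no row named for caregiver burden or number of treatments, so how often these are recorded in the extension cannot be read from it.

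**The concern.** The aim is about change over time. The model's stated purpose is the effect of patient characteristics. The protocol does not say which result answers the aim, and a reader will naturally look to the year coefficient.

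That coefficient has a different meaning depending on how the other covariates are entered. With current annual values it is the change left after removing whatever runs through sweat chloride, nutrition, caregiver burden and number of treatments. ETI is known to move at least the first two. Body image is one of the outcomes in this section, and nutritional status is an obvious route by which it could change. If such a route carried the change, the model would credit it to the covariate and could show little or no effect of year. Aim 7 could then be answered wrongly from a correctly fitted model.

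**Working it through.** **1. Is there a figure to reproduce?** No. The sample size section covers the parent study only, and no effect size, SD, power or alpha is stated for extension Aim 7.

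**2. The algebra.** Let the outcome have a direct yearly slope β. Let covariate k have coefficient γk and drift by δk per year within the period of observation.
- Total change per year = β + Σ γk·δk.
- Covariates entered as current values: the year coefficient estimates β.
- Covariates fixed at one time point: they are constant within a patient, so the year coefficient estimates β + Σ γk·δk, the total.
- The gap between the two is Σ γk·δk. It is zero if every δk is zero.

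Only drift within years 3 to 7 counts, because that is when the outcomes are measured.

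**3. What the documents say about drift.** Table 3 (participants aged 12 and over, first year on ETI; differences of the tabulated means):

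| Variable | Baseline to 6 months | 6 to 12 months |
|---|---|---|
| Sweat chloride | 44.92 − 85.78 = −40.86 | 44.23 − 44.92 = −0.69 (p = 0.7358) |
| BMI z score | 0.36 − 0.12 = +0.24 | 0.28 − 0.36 = −0.08 (p = 0.0484) |
| Weight z score | 0.32 − 0.07 = +0.25 | 0.27 − 0.32 = −0.05 (p = 0.1253) |

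ETI clearly moves sweat chloride and nutrition, but the large movement is over by 6 months, well before the first mental health measurement. Sweat chloride was then flat and BMI z score was still moving slightly. Nothing is reported for years 3 to 7, and nothing at all for number of treatments.

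**4. Illustration by simulation (all inputs assumed).** 200 patients, 5 yearly visits, 40 runs per scenario, random-intercept model. Effects on the outcome: 1 point per nutrition z score, 0.02 per mmol/L sweat chloride, 0.3 per treatment. Patient and residual SDs: 3 points each. The direct slope is 0.20 a year in scenarios a to c and 0 in d.

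| Scenario (drift per year) | True total slope | Year only | Covariates fixed at first visit | Current values |
|---|---|---|---|---|
| a. No drift | 0.20 | 0.195 | 0.195 | 0.193 |
| b. Sweat chloride −1 | 0.20 − 0.02 = 0.18 | 0.185 | 0.185 | 0.204 |
| c. Nutrition −0.1, treatments −0.5 | 0.20 − 0.10 − 0.15 = −0.05 | −0.034 | −0.034 | 0.203 |
| d. All three drifts, no direct slope | −0.10 − 0.02 − 0.15 = −0.27 | −0.274 | −0.274 | 0.001 |

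Simulation error of each mean is about 3/√(200 × 10)/√40 = 0.011, where 10 is the sum of squared deviations of the five visit years. The results follow the algebra: fixed covariates leave the slope alone, and current values remove the part they carry.

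**5. A range for one covariate (assumed).** If number of treatments fell by 0.2 to 0.4 a year and each were worth 0.3 to 0.5 points, the gap would be 0.2 × 0.3 = 0.06 to 0.4 × 0.5 = 0.20 points a year. Over the four yearly steps from year 3 to year 7 that is 0.24 to 0.80 points. With no fall it is zero.

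**The case against.** The strongest reply is that the protocol never says current values are used. Pre-ETI sweat chloride and nutrition exist, covariate timing is ordinarily settled in a statistical analysis plan (not shown here), and with fixed values the year slope is not distorted. The model also has its own legitimate purpose: the background promises to study how mental and physical health are related, and these covariates are needed for that. Finally, the general Statistical Analysis text promises descriptive statistics for all outcomes, analysis of means and trajectories over time, and mixed models adjusted for demographics and co-morbidity.

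Much of this stands, and it rules out four stronger readings that a reader might infer:
- *That the model certainly adjusts for on-treatment values.* This is the natural reading, because sweat chloride and height and weight are re-measured yearly alongside the questionnaires and only age is anchored. It is not stated.
- *That the 40.86 mmol/L fall in sweat chloride shows the slope is distorted.* That fall precedes every mental health measurement, and the level was flat from 6 to 12 months. Participants who interrupt ETI or change modulator may stay in the study, so later drift is possible, but it is not shown.
- *That ETI is shown to reduce the number of treatments.* The parent hypothesis is lower adherence to routine therapies, which is a different quantity. The remark about weight gain likewise concerns adherence to ETI, not mood.
- *That no other longitudinal analysis is planned.* The general text plans several.

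The reply does not remove the point. The general text is not tied to Aim 7, whereas the Aim 7 section fixes one covariate list for every mental health outcome. If that model serves only to study patient characteristics, the section names no analysis that answers its own aim. If it is meant to answer the aim, its year effect may not be the change sought.

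**Conclusion.** The point holds in a conditional form. The Aim 7 section secures no year effect free of variables measured after ETI began. If sweat chloride, nutrition, caregiver burden and number of treatments are entered as current annual values, the year coefficient differs from the total change by the sum of each coefficient times that covariate's drift within years 3 to 7. If they are fixed at one time point, or flat over those years, the difference is essentially nil.

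The size cannot be derived from the documents. The simulated slopes and the 0.24 to 0.80 point range rest wholly on assumed drifts and effects, and show only that the sign of the year effect can change.

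A separate limit applies whichever model is used. There is no mental health measurement before ETI, and with age at initiation held fixed, year also carries ageing. The data can describe change over years 3 to 7 on study. They cannot give change from before ETI or change attributable to ETI.

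**What to change.** For each mental health outcome:
1. Add a mixed model with year plus characteristics fixed before ETI (age at ETI initiation and genotype), and name its year effect as the Aim 7 change over years 3 to 7.
2. Keep the present model as a secondary analysis of association with patient characteristics. State that its covariates are time-varying and that its year coefficient is not the total change.
3. State that neither model estimates change from before ETI or an effect of ETI, since no earlier mental health data exist.

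The cost is one extra model per outcome and a few sentences of text. No new data are needed.

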Statistical analysis of longitudinal data requires methods that can properly account for the intra-subject correlation of response measurement. Preliminary analysis of treatment group means over the time periods will inform more complex analyses of derived variables such as slopes, pre/post analysis and response trajectory over time. Linear mixed models will include demographic and co-morbidity covariates to adjust for confounders. Random effects will account for correlation among repeated measurements. Data transformation and distributional assumptions will depend on the types of data. A Normal distribution will be assumed for continuous variables. A Poisson distribution and log transformation will be assumed for count data. Categorical data will be analyzed using logistic or multinomial regression where appropriate. Model diagnostics will be applied to assess model fit, distributional assumptions and potential outliers. Where distributional assumptions are not met, non-parametric alternatives will be employed. Where there are multiple outcome measures relating to a specific aim, multiple comparison adjustments may be necessary. False discovery rate (FDR) adjustments will be applied where appropriate.

Biosample Collection, Processing and Storage Plan For Parent Study

Blood

Blood (15ml) will be collected, where possible, during clinically indicated venepuncture. And aliquoted as follows:

- 5ml in EDTA tube for DNA extraction. Sample transferred to the lab and frozen at -80°C for later transfer to Central labs and thereafter to our collaborators in Toronto (FR). This sample will be used for the CF Canada funded genetic modifier study.
- 10ml (or the remainder) will be transferred to a serum tube and transferred to the laboratory for processing. Samples will be centrifuged at 3000rpm and the supernatant (serum) aliquoted to 5 separate 1.5ml
 Eppendorf tubes. Aliquots will be labelled and frozen at -80°C. These aliquots to be sent to central labs and stored for future use.
- For the year 1 blood collection, 10ml blood will be collected and processed as above, frozen at -80°C, and sent to central labs.

Nasal Lavage

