Eligibility Assessment	Х	Х															
Sweat Chloride		Х				Х		Х				Х	Х	х	Х	х	Х
LCI	Х	Х				Х		Х		Х		Х	Х	Х	Х	Х	Х
Spirometry-controlled CT (A*)		Х						Х				Х		X1		X1	
Height/Weight/BMI*	Х	Х			Х	Х	Х	Х	Х	Х	Х	Х	Х	Х	Х	Х	Х
FEV1*	Х	Х			х	Х	Х	х	Х	Х	Х	Х	Х	х	х	Х	Х
Airway Sampling (Micro)*	Х	Х			Х	Х	Х	Х	Х	Х	Х	Х	Х	Х	Х	Х	Х
Nasal Lavage (A*)		Х				Х		Х				Х	Х	х	х	Х	Х
FeNO	Х	Х				Х		Х									
Liver Function Testing*		Х			Х	Х	Х	Х				Х	Х	х	Х	Х	Х
Liver Ultrasound		Х						Х				Х	Х	Х	Х	Х	Х
Sputum Collection (A*)		Х				Х		Х		Х		Х	Х	х	Х	Х	Х
Liver Examination		Х						Х				Х					
Stool Collection		Х	Х			Х						Х	Х	х	Х	Х	Х
Blood Collection		Х						Х				Х	Х	Х	Х	Х	Х
Breath Sample Collection		Х			Х	Х	Х	Х									
Abdominal Symptom Score	Х	Х	Х	Х		Х		Х				Х	Х	х	Х	Х	Х
CFQ-R		Х				Х		Х				Х	Х	Х	Х	Х	Х
Pharmacy Records MPR								Х				Х					
Adherence Questionnaire	Х	Х			Х	Х	Х	Х	Х	Х	Х	Х					
MEMs Caps Reading (M)								Х				Х					
Antibiotic Use		Х						Х				Х					
Adverse Event Check			Х	Х	Х	Х	Х	Х	Х	Х	Х	Х	Х	Х	Х	Х	Х
Mental Health Questionnaire													Х	Х	Х	Х	Х

* Collected as normal clinical care,

A - Advanced arm testing in RECOVER parent study

¹ Only for patients who performed spirometry-controlled CT in parent study. Scan at years four and six at sites doing routine clinical CT. Scan at year six for sites not performing biennial CT

M - MEMs study only

Table 14. Schedule of assessments. Each visit has a study window. For the RECOVER parent study the baseline visit (0 month visit) will have an 8 week pre commencement on ETI start window. The 1, 2 and 3 month visits have +/- 2 week window. The 6, 9, 12, 15, 18, 21 and 24 month visits have +/- 1 month window. For the RECOVER extension study each annual visit will have a window of +/- 4 month.

Study Governance and Management Plan

RECOVER

[figure not shown]

Figure 6 RECOVER study management structure.

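### The mental health model fixes a random intercept only for up to five annual scores; if patients' courses differ, the standard error of the year trend will be too small

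*Protocol*

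**What the plan says.** Extension Aim 7 in the Protocol's list of specific aims reads "To determine the longitudinal changes in mental health outcomes associated with the use of ETI in children and adults with CF over a period" of five years. The section Specific Aim 7 for Extension Study – Mental Health then sets the model: "A linear mixed model for each of the mental health outcomes will be used to investigate impacts of patient characteristics over time". The covariates are listed in full: "Fixed effects in the model will be: age at ETI initiation, genotype, sweat chloride level, nutritional status, caregiver burden scores, number of treatments, year". The covariance structure is one sentence: "The model will use random intercept for patient". No random slope, serial-correlation structure or interaction with year is named, and the text does not say whether year is linear or categorical.

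Table 14 (Study Visit Timetable) marks the row "Mental Health Questionnaire" in each of Years Three to Seven and nowhere in the parent study, so a patient has at most five scores per instrument.

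The general analysis text under Statistical Analysis says "Random effects will account for correlation among repeated measurements" and "Model diagnostics will be applied to assess model fit, distributional assumptions and potential outliers". It also mentions slopes and response trajectories among possible analyses, but gives no rule that would change the mental health model.

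**The concern.** A random intercept implies that scores one year apart are as strongly correlated as scores four years apart, and that all patients share one slope. Over five years, in a cohort running from young children to adults who may interrupt or stop ETI and remain in the study, differing courses are plausible. The model would then treat between-patient variation in slope as independent visit-level noise and report too narrow an interval for the year trend, which is the quantity closest to the aim. A drift in depression or anxiety scores could be declared too readily.

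The second issue is what the fixed effects can show. For characteristics that do not change, such as age at ETI initiation and genotype, a main effect only moves the average level. If the question is whether the course differs by those characteristics, the listed model cannot estimate it.

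**Working it through.** The protocol states no power, standard error or alpha for this model, so there is no figure of its own to reproduce.

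**Inputs**
- Random intercept only, seven main effects: Mental Health section.
- Up to five annual visits: Table 14.
- r = slope variance / residual variance: not given; assumed range 0 to 0.5.
- Two-sided alpha of 5%, linear year and complete data: assumptions.
- Number of patients: cancels from the ratio below.

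**Linear year trend.** With k equally spaced visits and Sxx the sum of squared centred times:
- true variance of the slope is proportional to (1 + r·Sxx)/Sxx;
- the random-intercept model absorbs slope variation into its residual and reports (1 + r·Sxx/(k−1))/Sxx.

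For k = 5, centred times are −2, −1, 0, 1, 2, so Sxx = 10 and

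reported SE / true SE = √[(1 + 2.5r)/(1 + 10r)].

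Actual error = 2[1 − Φ(1.96 × ratio)].

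| r | SE ratio | Actual error at nominal 5% |
|---|---|---|
| 0 | 1.00 | 5.0% |
| 0.01 | 0.97 | 5.8% |
| 0.05 | 0.87 | 9.0% |
| 0.10 | 0.79 | 12.1% |
| 0.25 | 0.68 | 18.2% |
| 0.50 | 0.61 | 23.0% |

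Example at r = 0.10: √(1.25/2.00) = 0.79, so the reported SE is 21% too small. This r means a between-patient slope SD of √0.10 = 0.32 residual SDs per year. The ratio cannot fall below √(2.5/10) = 0.50. Simulation (20,000 data sets per setting, 150 patients) agreed with the closed form to within about half a percentage point, giving 12.4% at r = 0.10; a test that lets slopes vary held close to 5%.

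**Fewer visits.** For k = 3, Sxx = 2 and the ratio is √[(1 + r)/(1 + 2r)]. Errors are 5.5%, 6.1% and 7.4% at r = 0.05, 0.10 and 0.25. For k = 2 the ratio is exactly 1 and the error is 5.0%.

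**Serially correlated errors instead of varying slopes.** With five visits and AR(1) errors, the error for the linear trend is 8.1%, 11.7% and 15.5% at correlations of 0.2, 0.4 and 0.6.

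**Year as categorical.** For two visits d years apart, the ratio is √[(1 + 2.5r)/(1 + d²r/2)]. At r = 0.10:
- d = 4 (first to last): √(1.25/1.80) = 0.83, error 10.2%;
- d = 2: √(1.25/1.20) = 1.02, error 4.5%;
- d = 1: √(1.25/1.05) = 1.09, error 3.2%.

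Long contrasts are too narrow, the two-year contrast is about right and the one-year contrast is conservative.

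**Characteristic-by-year terms.** Added without a random slope, these carry the same inflation (12.0% at r = 0.10 and 18.0% at r = 0.25 in simulation), so the two changes belong together.

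**The case against.** A reader might infer that the model is wrong as written and that its standard errors will be too small. The documents do not support that. They give no variance components; if slopes do not vary and errors are not serially correlated, the standard error is correct. If year is categorical, which the text allows, some contrasts are conservative.

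Nor do five visits hold for everyone. The protocol limits the Pediatric Symptom Checklist to ages 5–17, PHQ-9 and GAD-7 to age 12 and over, and the PROMIS anxiety and mood scales to age 8 and over. A child aged 9 at the Year Three visit reaches 12 at Year Six and has at most two PHQ-9 scores; a 15-year-old has about three Checklist scores. For such patients the inflation is small or absent, and a random slope is harder to estimate. Adults can still supply five PHQ-9 and GAD-7 scores, so the point survives there.

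A reader might also infer that trajectories go untested. That too goes beyond the text: the year term estimates average change, and the general analysis section allows for slopes and trajectories. The model's purpose, "will be used to investigate impacts of patient characteristics over time", can be read as average associations with covariates updated each year, such as sweat chloride and nutritional status, which needs no interaction.

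Finally, mental health is not among the listed primary or secondary outcomes, and covariance detail is often left to an SAP. That lowers the weight but does not remove the point: the protocol chose to fix this structure, and the promised diagnostics carry no commitment to alter it.

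**Conclusion.** The concern holds conditionally. For a linear year trend with five complete visits, the random-intercept model is right at r = 0, barely off at r = 0.01 (5.8%), and clearly anti-conservative from about r = 0.05 (9%) to r = 0.25 (18%). Serial correlation produces inflation of similar size. First-to-last change is affected somewhat less, and short contrasts or short series little or not at all. These figures rest on assumed values of r, linear year unless stated otherwise, and complete data. The interaction issue applies only if differences in course by time-fixed characteristics are intended. This is a cheap improvement to a stated method for a longitudinal aim.

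**What to change.** Replace the sentence on the random intercept with: random intercept and random slope for year, or another suitable residual covariance, with participant-clustered robust standard errors if the slope variance cannot be estimated (for example for instruments with few visits per child).

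State whether year is linear or categorical, and what is meant by impacts over time. If differences in course by age at ETI initiation or genotype are the target, add those characteristic-by-year terms. If average associations with yearly updated covariates are meant, the main effects suffice.

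The cost is a wording change. It needs no new data, visits or patients. The downside is slightly wider intervals and occasional non-convergence, which the robust fallback covers.
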